1.0 Objectives

1.1 Describe the purpose, specific aims, or objectives of this research.

Response: The proposed research will translate research on delay discounting to the prevention of Type 2 diabetes (T2D) in persons with prediabetes. In this study, we will test our ability to engage and change the target, delay discounting (DD).

1.2 State the hypotheses to be tested, if applicable.

NOTE: A hypothesis is a specific, testable prediction about what you expect to happen in your study that corresponds with your above listed objectives.

Response: We predict that poverty conditions will increase discounting of the future for ERT subjects, but those receiving EFT will show levels of DD similar to levels observed for participants in the neutral condition. We also predict that EFT will activate brain regions associated with delay of gratification and prospection, and improve executive functions related to EFT, such as working memory.

2.0 Scientific Endpoints

2.1 Describe the scientific endpoint(s), the main result or occurrence under study.

*NOTE: Scientific endpoints are outcomes defined before the study begins to determine whether the objectives of the study have been met and to draw conclusions from the data. Include primary and secondary endpoints. Some example endpoints are: reduction of symptoms, improvement in quality of life, or survival. Your response should **not** be a date.*

Response: The primary endpoint is the reduction of discounting of the future and increase activation in regions associated with delay of gratification and prospection.

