Subjective Hunger: Participants will be asked to provide subjective ratings of their hunger. Hunger will be assessed using a 5-point Likert scale (anchored by 1-Extremely Full and 5-Extremely Hungry).

Subjective Preferences: Participants may be asked to provide subjective ratings of their food/activity preferences by ranking, rating their liking using a 5-point Likert scale (anchored by 1-Do not like and 5-Like very much), and making choices between their food/activity.

Same Day Food Recall: Participants will be asked if they are willing to eat the study food during a 24-hour recall questionnaire assessing past food behavior

(e.g. what time they ate their last meal, food items consumed in the past 24 hours, etc.). Those who say they are not willing to eat the study food will not be included in the study.

Cue Attention: A Likert-style scale assessing attentiveness to the episodic cues and vividness cues during tasks will be assessed on a scale from 1 to 5, where 1 indicates “not at all” and 5 indicates “very much”.

Delay Discounting: An operational definition of impulsivity is delay discounting, the degree to which a person will discount the value of a larger delayed reward in favor of a smaller immediate reward. Computerized/ experimenter administered assessments will provide participants with choices between a smaller amount of a hypothetical commodity available immediately or a larger amount available later. Participants will make choices between rewards such as money, food, physical activity, and health gains. Two methods will be used to measure discounting, Adjusting Amount and Adjusting Delay.

Adjusting Amount Discounting. The magnitude of the immediate commodity is adjusted until it is subjectively equivalent to the later larger amount. Subjective equivalence will be obtained at delays such as; 1 day, 1 week, 1 month, 3 months, 6 months, and 1 year. To ensure comparison between money and non-monetary rewards, prior to running the discounting programs for food, physical activity and health, participants will indicate the amount of the commodity whose receipt “right now” would be equally valuable to the participants as receiving a set amount of money, for example \$100.

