17.0 Data Management and Analysis

17.1 Describe the data analysis plan, including any statistical procedures. This section applies to both quantitative and qualitative analysis.

Response:

Analytic plan is to use factorial ANCOVA to compare between group differences in different measures of DD, executive function and fMRI-measured brain function for subjects randomly assigned to poverty/neutral conditions and EFT/ERT. Covariates will be used if significant differences between groups are observed in subject characteristics. We predict a main effect of neutral/poverty, such that those assigned to poverty will have higher DD than those assigned to neutral, and an interaction between poverty/neutral and EFT such that in the poverty condition, EFT will reduce the discounting to levels achieved by the wealth, ERT subjects. We also predict when participants who receive EFT under challenge of poverty that EFT will increase activation in brain regions associated with delay of gratification (LPFC and AC) and prospection (hippocampus) relative to those who receive EFT under similar challenges.

17.2 If applicable, provide a power analysis.

NOTE: This may not apply to certain types of studies, including chart/records reviews, survey studies, or observational studies. This question is asked to elicit whether the investigator has an adequate sample size to achieve the study objectives and justify a conclusion.

Response:

The sample size is based on our studies of EFT versus ERT on DD in overweight and obese subjects, which showed an average AUC of $0.54 + 0.28$, and our unpublished research that poverty simulations reduces DD by 34%. We estimate in the ERT condition, neutral simulations will lead to less discounting and higher AUC than poverty simulations (0.54 vs 0.36). We estimate in EFT conditions, that simulations of neutral are associated with a small improvement in discounting in comparison to poverty simulations (0.63 vs 0.54). These predictions suggest that DD in EFT/Poverty and ERT/Wealth will be equivalent. The effect size for this interaction is 0.35. Using the overall SD we observed of 0.28, alpha of .05 and power of 0.80, we can show the effect size for this interaction with 17 Ss/group, or 68 total, or 34 per site in the behavioral portion and in the imaging portion. To be conservative, we will study up to 100 subjects.

17.3 Describe any procedures that will be used for quality control of collected data.

Response:

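### The plan names no primary discounting measure, contrast, success rule or multiplicity control, so the type I error of the primary claim is not controlled

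*Combined protocol and SAP*

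**What the plan says.** Section 2.1 states: "The primary endpoint is the reduction of discounting of the future and increase activation in regions associated with delay of gratification and prospection". It lists no secondary endpoint and does not say whether both parts must succeed or one is enough.

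Section 10.3 opens up the discounting part. On method it says: "Two methods will be used to measure discounting, Adjusting Amount and Adjusting Delay". On commodities, which it gives only as examples, it says: "Participants will make choices between rewards such as money, food, physical activity, and health gains". It adds that the adjusting-delay task is to be run with the same reinforcer types and magnitudes as the traditional tasks.

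Section 17.1 plans factorial ANCOVA to "compare between group differences in different measures of DD, executive function and fMRI-measured brain function". It names LPFC, AC and hippocampus for activation. For discounting it predicts both a poverty main effect and a poverty by EFT interaction. It designates no primary measure or contrast, and sets no significance threshold, hierarchy or adjustment.

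AUC and alpha appear only in the sample-size text of Section 17.2. Its inputs are an interaction effect size of 0.35, an SD of 0.28, alpha .05 and power 0.80. Its conclusion reads: "we can show the effect size for this interaction with 17 Ss/group, or 68 total, or 34 per site". The same number is applied to both portions of the study.

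**The concern.** A primary endpoint should fix, before the data are seen, which test decides the claim. Here the discounting part can be read from several measures and two factorial effects, and the activation part from three regions. Nothing in the plan prevents the claim from resting on whichever of these turns out significant. The power statement describes one test of one AUC outcome, so it does not describe that procedure.

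The imaging contrast is unclear as well. Section 4.1 randomizes the fMRI arm to EFT or ERT only, with no poverty factor. Section 17.1 nevertheless predicts activation under a poverty challenge, and it compares EFT recipients with other EFT recipients.

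What is at stake is whether a reported positive primary result can be read at the 0.05 level.

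**Working it through.** **The plan's own figure.** Inputs from Section 17.2: effect size 0.35 (read as Cohen's f), alpha .05, power 0.80, four groups. For a 1-df F test with noncentrality N × f², the smallest N is 67, which is 17 per group or 68 in total. At 68 the noncentrality is 68 × 0.35² = 8.33 and power is 0.81. The stated 68 is reproduced as the size for **one** test at 0.05.

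**Counting candidate tests.**
- Lower count: 2 discounting methods + 3 regions = 5.
- Upper count: 2 methods × 4 named commodities = 8, plus 3 regions = 11. The four commodities follow a *such as*, so 8 is inferred.
- Between: Section 10.3 also describes the adjusting-delay task as measuring monetary discounting. If it is run for money only, there are 4 + 1 = 5 discounting tests, or 8 with the regions.
- Executive-function tests and the second factorial effect are left out.

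**Scenario A: any result significant at two-sided 0.05 counts.** With independent tests the error is 1 − 0.95^k:
- 5 tests: 0.226
- 8 tests: 0.337
- 11 tests: 0.431

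With common correlation ρ within discounting and within regions, and the two arms independent, the error is 1 − (1 − error for discounting)(1 − error for regions). At ρ = 0.5 with 8 + 3 tests this is 1 − (1 − 0.250)(1 − 0.125) = 0.344. The correlated rates come from equicorrelated normal test statistics.

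| Tests | ρ = 0 | ρ = 0.5 | ρ = 0.7 | ρ = 0.9 |
|---|---|---|---|---|
| 2 + 3 | 0.23 | 0.20 | 0.18 | 0.15 |
| 5 + 3 | 0.34 | 0.29 | 0.24 | 0.18 |
| 8 + 3 | 0.43 | 0.34 | 0.28 | 0.19 |

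**Scenario B: as A, but only results in the predicted direction count.** Each test then contributes 0.025. Eleven independent tests give 1 − 0.975^11 = 0.24, and ρ = 0.9 gives 0.10. Five tests give 0.12 and 0.08.

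**Scenario C: both parts are required.**
- One named measure per part: at most 0.05.
- Any of 8 discounting measures and any of 3 regions, both effects null, independent: 0.337 × 0.143 = 0.048.
- Same rule, activation real (and almost certain to be detected), discounting null: the error is that of the discounting part alone, 0.34 at ρ = 0, 0.25 at 0.5, 0.19 at 0.7 and 0.12 at 0.9. In the predicted direction only, it runs from 0.18 down to 0.06.

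**The case against.** The strongest reply is that the plan never says any single result is enough. Section 2.1 joins the two parts with *and*, and if each part had one named measure the error would be at most 0.05. This is right as far as it goes, but the measures are not named. As Scenario C shows, requiring both parts does not protect the discounting claim if any discounting measure may serve.

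A reader might go further and infer that all the tests are run at 0.05, that any of 11 can be called a primary success, and that the error is therefore several times alpha. The documents do not support that as fact. The .05 is stated once, as a power input. No per-test or imaging threshold is given. The count of 11 rests on an open list of commodities. The endpoint is also directional, so two-sided rates are about twice the rate of false claims in the predicted direction. These points limit how firmly a size can be stated. They do not supply the missing specification.

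It can also be said that this is a mechanistic study of target engagement, in which many measures are expected and the choice between Holm and FDR is partly preference. That is fair for the secondary measures. It does not remove the need to say which result decides the primary claim.

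**Conclusion.** The concern holds as a gap in specification. Sections 2.1 and 17.1 fix no primary discounting measure, contrast, success rule or multiplicity control, so the type I error of the primary claim is not controlled.

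Its size is conditional. If any nominally significant result counts, the error is about 0.15 to 0.23 for 5 tests and 0.19 to 0.43 for 11, over within-domain correlation 0.9 to 0. For 11 tests it is 0.10 to 0.24 if only the predicted direction counts. If both parts are required but any discounting measure may serve, it can still reach 0.12 to 0.34 when only activation is real.

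The number of tests, their correlation, the independence of the arms and the 0.05 threshold per test are assumptions. No single multiple of alpha can be attributed to the plan.

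**What to change.** In Sections 2.1 and 17.1, name one primary per arm and state that each arm's claim stands on its own.

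- **Behavioral arm:** discounting AUC at session 2, tested by the poverty by EFT interaction at alpha .05. Section 17.2 says only AUC. Adjusting-amount with money is proposed here, and the sponsor should confirm that this is the AUC used for sizing. The session should be confirmed too, because the fMRI text in Section 10.1 implies that the behavioral arm does the thinking task at its first visit.
- **fMRI arm:** EFT versus ERT activation in LPFC, AC and hippocampus, with Holm correction across the three, once Section 4.1 (no poverty factor in this arm) and Section 17.1 (activation under poverty) are reconciled.
- **Secondary:** other commodities, k-values, the poverty main effect and executive-function tests.

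**Cost.** A few sentences, with no new data. The behavioral test keeps alpha .05. Each region loses some power: for an effect of f = 0.35, Holm's first step (0.05/3 = 0.0167) lowers power from 0.81 to 0.67 at 68 subjects and from 0.93 to 0.85 at 100. The documents give no imaging effect size, so this is only an illustration. With two separate claims, the chance of at least one false claim across arms is up to 1 − 0.95² = 0.0975. If one study-level claim is wanted, either require both or use 0.025 for each; at f = 0.35 the latter needs 84 subjects with equal groups.

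**A caution when naming the interaction.** The four AUC means in Section 17.2 with SD 0.28 give f = 0.35 for the overall comparison of four groups. The interaction contrast is (0.54 − 0.36) − (0.63 − 0.54) = 0.09, so its f is 0.09/(4 × 0.28) = 0.08, with power of about 0.10 at 68 subjects. This is separate from multiplicity, but the sizing should be revisited in the same edit.

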3.0 Background

3.1 Provide the scientific or scholarly background, rationale, and significance of the research based on the existing literature and how it will contribute to existing knowledge. Describe any gaps in current knowledge. Include relevant preliminary findings or prior research by the investigator.

Response: DD has been related to several adverse health behaviors including smoking (Bickel et al., 1999) and obesity (Rollins et al., 2010). Our laboratories have extensive experience collecting information about DD and these various health outcome behaviors.

Initial research on Type 2 diabetes (T2D) using a brief monetary choice questionnaire showed T2D individuals who discount the future have worse metabolic control than those who delay gratification (Reach et al., 2011). To our knowledge, there has been no research on the effects of EFT on DD among patients with prediabetes.

Adults with greater DD is associated with obesity (Appelhans et al., 2012), and low activation of brain sites critical for self-control in DD predicts longitudinal weight gain in adults (Kishinevsky et al., 2012). Likewise, inability to delay gratification predicts greater subsequent weight gain in young children (Francis and Susman, 2009) and poorer response to evidence-based pediatric weight control programs (Seeyave et al., 2009).

In turn, the prevalence of T2D is associated with obesity (Kahn et al., 2006). Moreover, T2D (Vanhanen et al., 1997, Kanaya et al., 2004, Yaffe et al., 2004) and risk for T2D (Vanhanen et al., 1997) are associated with increased risk of executive dysfunction. This association suggests one of two possibilities: (1) diabetes causes a decline in executive function, or (2) inadequate executive function contributes to obesity and then diabetes. In either case, the relationship between executive function and both obesity and diabetes can present challenges in adhering to behavioral and medical therapies (Smith et al., 2011, Primožič et al., 2012). Poor planning, low working memory, cognitive inflexibility, poor attention to detail in combination with excessive DD can lead to weight gain and poor metabolic outcomes.

4.0 Study Design

4.1 *Describe and explain the study design (e.g. case-control, cross-sectional, ethnographic, experimental, interventional, longitudinal, observational).*

Response: This study is an experimental between-subjects design; subjects in the behavioral arm will be randomized to poverty/neutral scenarios crossed with EFT/ERT in a 2 x 2 factorial design. Subjects in the fMRI arm will be randomized to one of two groups: episodic future thinking (EFT) versus episodic recent thinking (ERT) control.

5.0 Local Number of Subjects

5.1 *Indicate the total number of subjects that will be enrolled or records that will be reviewed locally.*

Response: Up to 100-150 subjects will be enrolled (up to 250 nationally) with 50-75 enrolled in each arm of the study. In addition, a small sample (approximately 4-6 subjects) will be assigned to be pilot participants to help with quality assurance and data validity procedures. Participants will be informed if they are a pilot participant at the time of consent.

5.2 *If applicable, indicate how many subjects you expect to screen to reach your target sample (i.e. your screen failure rate).*

Response: We expect to screen approximately 250 subjects to reach our target sample with about a 40% attrition expected based on the screen fail rate and a 50% MRI ineligible rate from the previous two studies, MINDD 1 (Aim 1) and MINDD 2 (Aim 2).

5.3 *Justify the feasibility of recruiting the proposed number of eligible subjects within the anticipated recruitment period. For example, how many potential subjects do you have access to? What percentage of those potential subjects do you need to recruit?*

Response: The Division of Behavioral Medicine has access to a password protected database that has been approved for use by previous IRB committees (385420, 389912, 385442030-796526, STUDY00000936). This is a large database of people interested in participating in future studies. Research staff has extensive experience using the database for recruitment purposes and we feel confident that we can recruit the required number of subjects from this database and through our community based efforts. In addition, physicians will refer people from their clinics that may be interested in participating.

6.0 Inclusion and Exclusion Criteria

6.1 *Describe the criteria that define who will be **included** in your final study sample.*

NOTE: This may be done in bullet point fashion.

Response: Adults: Participants must be 18 years of age or older to participate.

Prediabetes: Participants must have a diagnosis of prediabetes within the last 2 years or meet criteria for prediabetes or meet criteria for prediabetes during screening for the study. The American Diabetes Association guidelines (Group, 2003) defines prediabetes as Fasting Plasma Glucose

(FPG) 100-125 mg/dl, 2h glucose 140-199 mg/dl after Oral Glucose Tolerance Test (OGTT), or hemoglobin A1c (HbA1c) approximately 5.7-6.4%.

6.2 Describe the criteria that define who will be **excluded** from your final study sample.

NOTE: This may be done in bullet point fashion.

Response: Type 2 Diabetes: Individuals will be excluded if they have Type 2 Diabetes.

Pregnancy: Women who are pregnant or lactating will be excluded from participation.

Substance use, abuse, or dependence: Individuals that currently have problems with substance dependence, addiction, or problematic substance use that would limit participation (e.g., binge drinkers, alcoholics, daily recreational stimulant/opiate users) will be excluded.

Conditions that affect adherence: Participants should not have a condition that would limit participation which include medical conditions that would affect individuals' ability to use the computer for prolonged period of time; leave the individual unable to ambulate; or current diagnoses of an eating disorder (anorexia, bulimia), unmanaged psychiatric disorder (depression, anxiety, attention deficit hyperactivity disorder (ADHD), schizophrenia), or an intellectual impairment that would impact study adherence.

Abnormal glucose related to medications: Participants should not be taking medications that would limit participation and cause abnormal glucose levels (e.g. atypical antipsychotic medications or glucocorticoids) including diabetic drugs such as Metformin.

Unwilling or unable to eat study food: Participants who are unwilling or not able to eat the study food (a PowerBar) will not be able to take part in this study.

Prior participation in similar studies: Individuals who have recently participated in a laboratory study using similar methods may also be excluded.

Anyone who cannot have an MRI (e.g. anyone who has any type of metallic implant in his/her body, including pacemakers, aneurysm clips, shrapnel, metal fragments, orthopedic pins, screws or plates, IUD's or piercings that cannot be removed) will not be able to participate in the imaging portion of the study (3b). Those who cannot have an MRI may be eligible to participate in the behavioral version of the study.

Do not meet discounting criteria: Individuals who do not meet discounting criteria (e.g. nonsystematic discounting) on a delay discounting task may be excluded.

6.3 Indicate specifically whether you will include any of the following special populations in your study using the checkboxes below.

NOTE: Members of special populations may not be targeted for enrollment in your study unless you indicate this in your inclusion criteria.

Response: Individuals who are not yet adults, adults unable to consent, pregnant women, and prisoners will be excluded from this study.

- Adults unable to consent
- Individuals who are not yet adults (infants, children, teenagers)
- Pregnant women
- Prisoners

6.4 *Indicate whether you will include non-English speaking individuals in your study. Provide justification if you will exclude non-English speaking individuals.*

*In order to meet one of the primary ethical principles of equitable selection of subjects, non-English speaking individuals may **not** be routinely excluded from research as a matter of convenience.*

In cases where the research is of therapeutic intent or is designed to investigate areas that would necessarily require certain populations who may not speak English, the researcher is required to make efforts to recruit and include non-English speaking individuals. However, there are studies in which it would be reasonable to limit subjects to those who speak English. Some examples include pilot studies, small unfunded studies with validated instruments not available in other languages, studies with numerous questionnaires, and some non-therapeutic studies which offer no direct benefit.

Response:

This study will not include non-English speaking participants. Since all the materials in this study will be in English, and the validated measurements are not provided in other languages, we will be excluding individuals who do not speak English.

